**Step 4:** *For participants on PrEP*, the study nurse performs a blood draw for creatinine clearance and a finger prick for DBS testing for adherence measures and (if applicable for this visit). See Table 1 for study calendar.

**Step 5 (for women on PrEP):** At each visit the study counselor will ask, and record responses, all participants on PrEP about any side effects associated with TDF/FTC, including diarrhea, nausea, fatigue, headache and rash (which are seen in about 10% of participants during the initiation of therapy). We will encourage participants to contact the study nurse if they experience side effects between visits.

**PrEP retention methods to improve adherence:** Each study visit will include counselling from peer counsellors who will discuss the importance of retention and adherence to PrEP for effectiveness. We will adapt messages from ongoing PrEP studies conducted by co-I [name] and team. We will also provide participants with a brochure to take home that discusses retention, adherence and side effects of PrEP. Each visit will include group and individual counselling. Group counselling will be led by a mother who has successfully taken PrEP for 3+ months to guide a discussion about the importance of retention, reminders on how to take the medication daily and how to address side-effects (e.g. nausea, headaches, etc).

**Step 6:** PrEP provision (for 1 or 2 months) and appointment reminder

*Follow-up & retention:* Tracing information will be taken at the enrolment visit and updated at each study visit. Retention activities will focus on scheduled measurement visits. Following our established approach in this

setting, we will provide reminder calls to participants before their measurement visits, and initiate tracing, including home visits, for women who do not attend the measurement visit within one week of the scheduled visit.

*PrEP provision:* monthly for the first 3 months, and then 2-months intervals after that. Participants on PrEP will have regular monitoring with laboratory tests, including creatinine levels to check for changes in renal function and dried blood spots (DBS) for adherence measures. Those with HBsAg+ will be excluded from the study. We will test for HIV seroconversion at every study visit.

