#### *Survey measures*

At study measurement visits, questionnaires will be administered to mothers participating in the study. Following standard procedures, the questionnaires will be translated into isiXhosa and Afrikaans and back translated to ensure appropriate phrasing. Questionnaires will include:

- Basic demographic information and obstetric history (enrollment only)
- Partner's HIV status
- Sexual behaviors in the past month and week including # of sex partners, type of sex, and frequency of sex and condom use
- Substance use information using the AUDIT-C and DAUDIT scales
- Risk perception scales
- Partner, community and social support for PrEP
- For PrEP users, questions related to PrEP adherence according to self-report (the 3-day and 1-month recall and a visual analog scale) and pharmacy-based pill counts will be conducted at each study measurement visit.

- Additional schedules will be used to collect data on symptoms in mothers that are potential side-effects of PrEP use (at all study visits)
- We will also use short questionnaires to collect data on all women's experiences in the study, and the acceptability of the PrEP initiation, including what kind of services were offered at each visit (e.g. counseling, peer mentorship, and IEC materials, medication)
- Self-reported symptoms related to STIs
- This will focus on the positive and negative aspects of their experiences of PrEP initiation in pregnancy and breastfeeding and any factors associated with PrEP initiation, retention, and adherence.

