For **Aim 1**, each outcome will be described via cumulative incidences at fixed intervals (e.g., cumulative PrEP initiation by delivery) and incidence densities over time. The general statistical approaches to these outcomes are analogous; data will be described graphically, including product-limit graphs, with preliminary analyses based on standard approaches for rates and proportions. To address aims 1 and 2, the modelling approach will vary depending on the nature of the outcome. **PrEP initiation** will be modelled using a probit model (preferred to estimate risk factors for common outcomes) with individual-level covariates as fixed effects; when time-dependent or visit-specific covariates are included in the analysis of cumulative initiation (for **Aim 2**) we will shift to a mixed-effects setting with random effects around individual participants. **PrEP retention** will be examined using similar approaches; in addition, we will use time-to-event methods to estimate factors associated with time to loss (non-retention) among women having initiated PrEP. **PrEP adherence** will be modelled using mixed effects probit models as above and generalized estimating equations to examine the marginal effect of individual-level covariates on adherence during the study [85]. Throughout, robust estimates of standard errors will be used.

The same modelling approaches will be used to explore secondary implementation questions (**Aim 2**) such as the effect of individual, pill/study, and disease factors on PrEP initiation, retention and adherence outcomes (see Figure 1 for conceptual model). The main exposures include: **individual level factors**: risk perception, community/family support, sexual activity, risk, concerns about drug's side effects and harm on self

(pregnancy) and/or infant's health. **Pill regimen and study factors** include: PrEP side effects, time required to participate in study, patient-provider relationship measured from the participants' perspective. **Disease factors** include: stigma around HIV and PrEP, and partner's HIV status (see Table 5 for specific variables).

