### The objectives of the study are to:

**AIM 1:** Determine the distribution of women across the PrEP cascade (initiation, continuation and persistence on PrEP) and outcomes (maternal HIV incidence, infant HIV incidence, and adverse events) in a cohort of pregnant and breastfeeding women using quantitative and qualitative approaches

- (1) Determine the distribution of women across the PrEP cascade and outcomes including HIV acquisition (maternal and infant) and adverse events
  1. PrEP initiation: defined PrEP start at any time point in the study
  2. PrEP continuation: defined as return to clinic and PrEP refill within 45 days post initiation
  3. PrEP persistence: defined as reporting taking PrEP in  $\geq 5$  out of last 7 days or  $\geq 25$  out of last 30 days (self-reported), or  $\geq 600$  fmol/punch from DBS TDF-DP (objective report)
- (2) Evaluate key predictors of PrEP initiation, continuation and persistence on PrEP including age, substance use, relationship status and partner's serostatus

**AIM 2:** Evaluate patient and provider-level factors associated with the PrEP cascade using quantitative and qualitative approaches

- (1) Evaluate individual-level factors (including risk perception, substance use, sexual activity, and partner/family/community encouragement) associated with PrEP initiation, continuation and persistence on PrEP
- (2) Evaluate pill and study factors (including PrEP-related side effects, time to participate in study, participant-provider communication) associated with PrEP initiation, continuation, and persistence on PrEP
- (3) Evaluate disease factors (including partner's HIV status, HIV-related stigma) associated with PrEP initiation, continuation, and persistence on PrEP

**AIM 3:** Apply an established mathematical model to simulate the impact of improvement in the PrEP cascade on HIV infections averted (maternal and perinatal)

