For *Aim 2*, the same modelling approaches will be used to explore secondary implementation questions such as the effect of individual, pill/study, and disease factors on PrEP initiation, continuation and persistence outcomes. The main exposures include: individual level factors: risk perception, community/family support, sexual activity, risk, concerns about drug's side effects and harm on self (pregnancy) and/or infant's health. Pill regimen and study factors include: PrEP side effects, time required to participate in study, patient-provider relationship measured from the participants' perspective. Disease factors include: stigma around HIV and PrEP, and partner's HIV status.

For *Aim 2* qualitative data analysis, following our standard practice, study tools including in depth interview guides and survey materials will be translated into isiXhosa and Afrikaans, the predominant local languages, with independent back-translation for verification. We will digitally record the IDIs and then have the recordings transcribed verbatim. The recordings will be reviewed and verified for accuracy by the interviewers. Transcripts will then be translated and key quotations back-translated to verify meaning. A subset of 20% of transcripts will be double-coded to examine the inter-rater reliability of the coding process. After coding, Investigators will search by substantive codes and themes identified utilizing matrices to organize and allow for comparisons by group (e.g. age, pregnancy stage, partner status, initiators and non-initiators). Patterns in the matrices will be used to identify themes. Tables of themes will be created using the verbatim quotations as evidence to support the themes that serve as the primary data analyses approach. Conclusions will be based on interpretation of these tables of themes with quotations. Data will be managed using NVivo Software (QSR International).

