**Methods/Approach:**

See **Table 1** for precise definitions of prevention effective PrEP continuation and persistence

- (1) *Secondary analysis:* Describe each outcome listed above via cumulative incidences at fixed intervals (e.g., cumulative PrEP continuation after 1 year in study) and incidence densities over time. The general statistical approaches to these outcomes are analogous to the primary outcomes (above). Data will be described graphically, including product-limit graphs, with preliminary analyses based on standard approaches for rates and proportions.
- (2) Other analysis approaches on the PrEP cascade:
  - a. When time-dependent or visit-specific covariates are included in the analysis of cumulative PrEP initiation we will shift to a mixed-effects setting with random effects around individual participants.

Other outcomes (secondary outcomes):

- a. **Predictors of attrition at key steps in the PrEP cascade:** Methods will involve mixed methods analysis. Utilizing the qualitative data from the IDIs at month 7 and 12 of the study from a random selection of 60 participants (30 randomly selected from those who initiated PrEP and 30 randomly selected from those who chose not to initiate) to complement the quantitative data to understand factors associated with PrEP persistence and non-persistence, including 1) individual factors, (including risk perception, sexual activity and risk, substance use, and partner/family/community discouragement), 2) the pill regimen (side effects and concerns about adverse pregnancy or infant outcomes) AND patient-provider relationship and 3) the disease-related factors (including reasons behind stigma associated with PrEP taking).
  - i. **Individual factors:** Collected from CRFs in all participants (regardless of PrEP uptake) including: risk perception, sexual activity and risk, substance use, partner/family/community discouragement, sociodemographic variables, relationship characteristics and fear about adverse pregnancy and/or infant health outcomes. Collected from the sub-set of women participating in the IDIs.
  - ii. **Pill/study factors:** Collected from CRFs in participants who decide to take PrEP, including: side effects on PrEP, and barriers to attending frequent study visits and DBS during those visits, and provider participant communication and support

(measured from participant perspective). Collected from the sub-set of women participating in the IDIs.

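### Aim 2 relates PrEP side effects to PrEP initiation, but they can arise only after a first start; for 45-day continuation, non-returners have no scheduled side-effect record

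*Combined protocol and SAP*

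**What the plan says.** The pairing with initiation appears three times.

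- SAP section 1, Aim 2(2): "Evaluate pill and study factors (including PrEP-related side effects, time to participate in study, participant-provider communication) associated with PrEP initiation". Continuation and persistence follow in the same sentence.
- SAP section 1, statistical considerations for Aims 1 and 2: "the effect of individual, pill/study, and disease factors on PrEP initiation, continuation and persistence outcomes". PrEP side effects are listed there under pill regimen and study factors.
- Protocol section 6, statistical analysis considerations: "the effect of individual, pill/study, and disease factors on PrEP initiation, retention and adherence outcomes".

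On who supplies the data, SAP section 2.5 says of pill/study factors: "Collected from CRFs in participants who decide to take PrEP, including: side effects on PrEP". Visit burden and provider communication are in the same item. Individual factors, by contrast, are "Collected from CRFs in all participants (regardless of PrEP uptake", and the disease-factor item likewise covers all participants. Protocol section 5, follow-up Step 5, reads: "At each visit the study counselor will ask, and record responses, all participants on PrEP about any side effects associated with TDF/FTC". The protocol's survey list is wider: it also gathers all women's experience of the study and the services they were offered.

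Continuation has two definitions. Under Aim 1 in SAP section 1 it is a clinic return with a refill inside 45 days of starting. In the statistical considerations, the study measures and SAP Table 1 it is at most one missed visit. The first scheduled return after starting is at 1 month (protocol section 5, enrolment Step 10).

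**The concern.** A predictor has to exist before the outcome it predicts. PrEP side effects do not exist before a first start, so the planned model either has no variation in its outcome or compares women who could have the exposure with women who could not. The second case is the more dangerous one. Software may return a number, and it would read as side effects raising uptake.

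For continuation the question is whether side effects are recorded before the event. The protocol's counselling text (enrolment Step 1) expects side effects in the first 1-2 weeks, whereas the first scheduled record comes at 1 month. Under the 45-day definition that same visit decides the outcome, so a woman who stops early because of side effects may leave no scheduled record of them.

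**Working it through.** **Inputs.** From SAP section 2.2: N = 1200, 60% initiate, 75% of those continue at 12 months, and 70% of those adhere. From the protocol's background section on side effects: about 10% of starters. The 5% to 30% range below is an assumption.

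**1. The plan's own counts.** 1200 × 0.60 = 720; 720 × 0.75 = 540; 540 × 0.70 = 378. All three match the SAP. It follows that 1200 − 720 = 480 women do not initiate and 720 − 540 = 180 initiators do not continue.

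**2. Initiation, women with a side-effect value only.** All 720 are initiators. The outcome is 1 throughout and no association can be estimated.

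**3. Initiation, non-initiators coded as no side effects.** At 10%, 720 × 0.10 = 72 women have a side effect.

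| | Initiated | Did not | Total |
|---|---|---|---|
| Side effect | 72 | 0 | 72 |
| None | 648 | 480 | 1128 |

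Relative risk = (72/72) ÷ (648/1128) = 1 ÷ 0.574 = 1.74. For a side-effect rate r the formula is RR = (1200 − 720r) ÷ [720(1 − r)]:

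- r = 5%: 1164/684 = 1.70
- r = 20%: 1056/576 = 1.83
- r = 30%: 984/504 = 1.95

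The result depends only on the uptake and side-effect rates and carries no information about why women start. Every woman with a side effect is an initiator, so the data are separated. A probit fitted to this table did not converge (coefficient 8.1, standard error about 1.9 million).

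**4. Continuation under the 45-day rule.** Women who do not return have no scheduled side-effect record. A one-visit lag does not help, because it reaches back only to enrolment, before any dose. As an illustration, apply the 75% (which the plan gives for 12 months) to this outcome, with 10% side effects in the 540 continuers (54 women). Let f be the unknown share with side effects among the 180 non-continuers, and b = 180f. Then RR of non-continuation = [b/(54 + b)] ÷ [(180 − b)/(666 − b)], where 666 = (540 − 54) + 180.

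| f | b | RR |
|---|---|---|
| 0% | 0 | 0 |
| 5% | 9 | 0.55 |
| 10% | 18 | 1.0 |
| 20% | 36 | 1.75 |
| 50% | 90 | 4.0 |

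Return-visit data do not identify f, so they do not identify even the direction of the association.

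**5. Continuation under the missed-visit rule.** Failure needs more than one missed visit, so most women have earlier attended visits with recorded values. These can serve as lagged covariates. Neither document states a lag.

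**The case against.** Four counter-arguments have weight.

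- **Most of the domain can precede a start.** Women not on PrEP attend visits and are asked again whether they want to start. Initiation may occur at any time, and the SAP plans visit-specific covariates for cumulative initiation. The protocol surveys all women's study experience, and the SAP's interview sample includes non-initiators. A reader might infer that no pill/study factor can be related to initiation; the documents do not support that. For time burden and provider communication, what remains is the conflict between SAP 2.5 and the protocol's survey list.
- **Symptoms are collected without a stated restriction to PrEP users.** The protocol has: "Additional schedules will be used to collect data on symptoms in mothers that are potential side-effects of PrEP use (at all study visits". In women who have never taken PrEP, however, these are background symptoms, so they do not rescue the initiation analysis. Re-initiation is allowed, and earlier side effects could be related to restarting, but the SAP specifies no such model.
- **Continuation has safeguards.** Censoring weights, multiple imputation, time-to-event methods, separate analyses of stopping, a table of reasons for ending treatment, tracing with home visits, and telephone interviews during lockdown are all planned. A reader might infer that continuation models fail in general, or that side effects will necessarily be understated as a cause of stopping. Neither follows: the missed-visit definition has usable earlier values, and under the 45-day definition the direction is unknown. The safeguards do not close the 45-day gap, because weighting and imputation cannot draw on side effects never recorded in non-returners, and no text makes tracing a systematic side-effect enquiry.
- **These are secondary, exploratory questions.** That is correct. No primary cascade proportion or sample size changes.

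**Conclusion.** The point holds in limited form. Relating PrEP side effects to first initiation is a stated analysis that cannot work: it has a constant outcome in 720 women, or a built-in relative risk of about 1.74 (1.70 to 1.95 for side-effect rates of 5% to 30%). That conclusion is logical and does not rest on the planning figures; only the size does.

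For time burden and provider communication the finding is an inconsistency between SAP and protocol over who is asked. For continuation it is serious mainly under the 45-day definition, where the illustrative relative risk runs from 0 to 4.0 as the unrecorded share goes from 0% to 50%. That illustration assumes 10% side effects in continuers and borrows the 12-month continuation figure. Under the missed-visit definition an unstated lag is the only gap. The correction should be made, but it affects Aim 2 and not the main cascade estimates.

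**What to change.** 1. **First initiation.** Remove PrEP side effects from this model in Aim 2(2) and in the statistical considerations of both documents. Use concern about side effects or harm instead, which SAP section 1 already lists as an individual-level factor. The individual-factor item in SAP 2.5 names fear of harm to pregnancy or infant; add concern about side effects there. Keep time burden and provider communication only as values recorded before the start. Women who start at enrolment will have little study experience to report.
2. **Who is asked.** Align the pill/study item in SAP 2.5 with the protocol's survey list, so that all women answer the study-factor questions.
3. **Missed-visit continuation and time to loss.** Take pill/study factors from the last attended visit before the interval being scored.
4. **45-day continuation.** Ask about side effects and the reason for stopping at the tracing contacts already planned for missed visits. Do not report a side-effect association for this outcome from return-visit data alone.

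The cost is SAP and protocol wording plus a short question at existing contacts. Lagged values are older than concurrent ones, and tracing will not reach every woman, so the number reached should be reported.

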## Sample size considerations

The projected sample size for the study is *1200 women enrolled from 1st ANC visit until 12-months postpartum (estimated mean of 18-months follow-up)*. This estimate is based on the following assumptions:

- (1) 60% of women will initiate PrEP during the study period (versus approximately 40% who will not);
- (2) Approximately 75% of women on PrEP will be retained in care at 12-months (defined as not missing >1 study visit among women on PrEP)
- (3) 70% of those retained in care (n=378) will adhere to PrEP during at-risk periods.

A sample size of 1200 women yields 80% power to detect identify a relative risk of 2.0 or greater in key covariates including age (<25 vs. >25 years), pregnancy and relationship status associated with PrEP initiation versus non-initiation. A sample size of 378 women (e.g. 70% of women retained in the study on PrEP will be adherent as measured by TDF-DP measures) yields 80% power to detect relative risks of 2.0 or greater associated with persistence in the cohort. The analysis will be based on women who complete the 12-month postpartum cohort follow up. We will use relative risk ratios performed at a two-sided  $\alpha$  level of 0.05.

## Statistical analysis considerations for AIMS 1 & 2

The primary analysis for *Aim 1* will focus on measuring the distribution of women across the PrEP cascade including: initiation, continuation and persistence. **PrEP initiation** will be based on a woman's uptake of PrEP and allow for stoppage and re-initiation; **PrEP continuation** will be defined as not missing >1 visit among those on PrEP (with separate analyses of PrEP stoppage). For **PrEP persistence** for women on PrEP we will measure both *perfect persistence* (i.e. level of objective persistence throughout pregnancy and breastfeeding periods) as well as "*prevention-effective*" persistence (i.e. persistence during times of sexual activity) in participants through objective and subjective measures to evaluate agreement between the two measures, and the level of under- or over-reporting. Primary persistence analyses will use objective measures (TDF-DP from DBS) taken on all those who enrolled and initiated PrEP; subsidiary analyses will consider (i) other persistence measures and (ii) multiple imputation for missing persistence data.

- **Measurement of use of PrEP:** Conducted through alternate definitions of the main outcomes (e.g. persistence by self-report versus persistence by pharmacy refill), compared using measures of agreement and will be analyzed as independent models to contrast estimated associations.
- **Measurement of prevention-effective execution:** Execution refers to PrEP persistence during a time when at-risk sex happens. It is calculated by: number of doses reported, or recorded/number of expected doses based on HIV risk and PrEP initiation/discontinuation
- **Prevention-effective continuation:** Prevention-effective continuation describes the duration of PrEP use during periods of HIV risk and references the absolute time of use during pregnancy and breastfeeding periods. We will adapt the methodology from previous PrEP studies in SA including FEM-PrEP to create a semi-ordinal composite persistence score from blood specimens from DBS every 2-months.  
For *Aim 1*, each outcome will be described via cumulative incidences at fixed intervals (e.g., cumulative PrEP initiation by delivery) and incidence densities over time. The general statistical approaches to these outcomes are analogous; data will be described graphically, including product-limit graphs, with preliminary analyses based on standard approaches for rates and proportions.

For *Aim 1*, we will also describe the frequency of HIV outcomes, including maternal HIV acquisition and MTCT, and any laboratory or self-reported side effects (e.g. changes in creatinine or self-reported side-effects [GI symptoms, headache, and etc.]). Analyses will include pure-count and person-time approaches; for the latter, confidence intervals will be calculated following the method of Breslow and Day. We will also describe infant outcomes over time (including birthweight, gestational age at delivery, pregnancy loss and any infant illness, hospitalization or death). While we expect the frequency of adverse HIV-related outcomes to be low, we will

describe characteristics of women who did/did not acquire HIV, and consider further analyses using the approaches outlined above.

To address *Aims 1 and 2*, the modelling approach will vary depending on the nature of the outcome. PrEP initiation will be modelled using a probit model (preferred to estimate risk factors for common outcomes) with individual-level covariates as fixed effects; when time-dependent or visit-specific covariates are included in the analysis of cumulative initiation (for *Aim 2*) we will shift to a mixed-effects setting with random effects around individual participants. PrEP continuation will be examined using similar approaches; in addition, we will use time-to-event methods to estimate factors associated with time to loss (non-continuation) among women having initiated PrEP. PrEP persistence will be modelled using mixed effects probit models as above and generalized estimating equations to examine the marginal effect of individual-level covariates on persistence during the study. Throughout, robust estimates of standard errors will be used.

For each outcome, covariates in the multivariable models will be selected a priori using directed acyclic graphs; the main exposures of interest include: age (<25 vs. >25 years old), pregnancy status (by trimester and pregnant vs. postpartum), relationship status (married/cohabiting vs. not) and substance use (vs. none). We will explore associations within subgroups of participants using interaction terms in predicting outcomes involving these four covariates in particular. Throughout the analysis of outcomes in the PrEP cascade, losses of patients at early stages are highly informative about outcomes later in the cascade. To specifically address this, we will perform further bias analyses with inverse probability of censoring weighting in addition to complete case analyses. We will also use multiple imputation via chained equations for missing data [83] to examine the potential impact of missing data.

For *Aim 2*, the same modelling approaches will be used to explore secondary implementation questions such as the effect of individual, pill/study, and disease factors on PrEP initiation, continuation and persistence outcomes. The main exposures include: individual level factors: risk perception, community/family support, sexual activity, risk, concerns about drug's side effects and harm on self (pregnancy) and/or infant's health. Pill regimen and study factors include: PrEP side effects, time required to participate in study, patient-provider relationship measured from the participants' perspective. Disease factors include: stigma around HIV and PrEP, and partner's HIV status.

For *Aim 2* qualitative data analysis, following our standard practice, study tools including in depth interview guides and survey materials will be translated into isiXhosa and Afrikaans, the predominant local languages, with independent back-translation for verification. We will digitally record the IDIs and then have the recordings transcribed verbatim. The recordings will be reviewed and verified for accuracy by the interviewers. Transcripts will then be translated and key quotations back-translated to verify meaning. A subset of 20% of transcripts will be double-coded to examine the inter-rater reliability of the coding process. After coding, Investigators will search by substantive codes and themes identified utilizing matrices to organize and allow for comparisons by group (e.g. age, pregnancy stage, partner status, initiators and non-initiators). Patterns in the matrices will be used to identify themes. Tables of themes will be created using the verbatim quotations as evidence to support the themes that serve as the primary data analyses approach. Conclusions will be based on interpretation of these tables of themes with quotations. Data will be managed using NVivo Software (QSR International).

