#### ***Methods/Approach:***

- (1) Study flow figure (see Continuation Flowcharts)
- (2) Number screened per week and month (target= 18 per week, 72 per month) vs number enrolled
  - a. The projected sample size for the study is 1200 women enrolled until 12-months postpartum (estimated mean of 18-months follow-up).
- (3) Subjects initiating PrEP compared to those who do not
  - a. Estimated that 60% of women (n=720) will initiate PrEP during the study period (versus approximately 40% who will not).
- (4) Continuation and persistence by group
  - a. Assumed that approximately 75% of women on PrEP (n=540) will continue on PrEP at 12-months (defined as not missing >1 study visit among women on PrEP);
  - b. Assumed that 70% of those retained in care (n=378) will adhere to PrEP during at-risk periods.
- (5) Final completion rates
  - a. Compare final number of participants who enroll in study, who initiate PrEP, who are retained in care, and who adhere to PrEP to sample sizes needed to yield 80% power (i.e., n=1200, 720, 540, 378, respectively).
- (6) Number of subjects in analysis data sets
  - a. Consider number of participants that will potentially be excluded from analyses because of withdrawal from study, missing data on key covariates or outcomes, etc.

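### The stated 80% power for a relative risk of 2.0 on PrEP initiation does not fit the plan's own 60% initiation rate; at realistic splits, 80% power corresponds to a relative risk of about 1.14 to 1.28

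*Combined protocol and SAP*

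**What the plan says.** The sample size paragraph appears in protocol section 6 and again, almost word for word, in SAP section 1. Its first assumption is "60% of women will initiate PrEP during the study period (versus approximately 40% who will not"). SAP 2.2, item 3a, repeats this as a count: "Estimated that 60% of women (n=720) will initiate PrEP during the study period".

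The power statement is "A sample size of 1200 women yields 80% power to detect identify a relative risk of 2.0 or greater in key covariates". The covariates named are age (under 25 against older), "pregnancy and relationship status associated with PrEP initiation versus non-initiation". The test level is given by "We will use relative risk ratios performed at a two-sided" alpha of 0.05. The same paragraph fixes the analysis set: "The analysis will be based on women who complete the 12-month postpartum cohort follow up".

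A parallel sentence claims 80% power for relative risks of 2.0 or more on adherence (persistence in the SAP) with 378 women. SAP 2.2, item 5a, then lists 1200, 720, 540 and 378 as the sizes needed for 80% power.

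No formula, reference-group rate or covariate split is given anywhere.

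**The concern.** A relative risk of 2.0 is very large for an outcome that 60% of women are expected to have. In two equal groups it means 80% against 40%, and 1200 women are far more than that contrast needs. The pairing of 80% power with 2.0 therefore looks like a calculation for a much rarer outcome.

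Predictors of initiation and persistence are a stated objective (SAP Aim 1(2) and Aim 2), and this paragraph is the only printed guide to how precisely they can be studied. A reader who relies on it will misjudge what an association of 1.2 or 1.3, or the absence of one, says about this cohort. SAP 2.2(5) also treats the same head-counts as thresholds for 80% power, so a shortfall could be misread as lost power for 2.0.

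**Working it through.** **Inputs from the documents.** N = 1200; overall initiation P = 0.60 (720 women); relative risk R = 2.0; two-sided alpha 0.05; stated power 80%.

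**Assumed.** The share f of women in the higher-uptake group, from 10% to 90%; and 900 or 540 as possible numbers analysed. The 900 is 75% of 1200, but the plan gives 75% only for women on PrEP. The 540 is the plan's count of women retained on PrEP, used here only as a low value.

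**Formulas.** With P fixed, the risks are p0 = P / (1 + f(R − 1)) and p1 = R × p0. Power is from the two-proportion z-test with pooled null variance: Φ[(p1 − p0 − 1.96·SE0) / SE1], where SE0 = √[P(1 − P)(1/n1 + 1/n0)] and SE1 = √[p1(1 − p1)/n1 + p0(1 − p0)/n0].

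**Step 1: try to reproduce the stated 80%.**
- f = 50%: p0 = 0.60/1.5 = 0.40, p1 = 0.80. SE0 = 0.0283, SE1 = 0.0258. z = (0.40 − 0.0554)/0.0258 = 13.3, so power is effectively 100%. About 46 women in total would give 80%.
- f = 90%: p0 = 0.60/1.9 = 0.316, p1 = 0.632. SE0 = 0.0471, SE1 = 0.0449. z = (0.316 − 0.092)/0.0449 = 4.98, so power exceeds 99.99%. About 210 women would give 80%.
- f = 20%: p0 = 0.50, p1 = 1.00. This is the limit; for smaller f, p1 exceeds 1 and R = 2.0 cannot occur.
- If 60% is read as the reference-group rate, R = 2.0 would need 120%.

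The 80% is recovered in only two ways. One is a lower-uptake group of about 20 of the 1200 women (1.7%). The other, at 50:50, is an overall outcome rate of about 5.5%. Other readings do not recover it for splits from 10:90 to 90:10. Non-initiation as the outcome gives at least 99.8%, and an odds ratio of 2.0 in place of the relative risk gives 92% or more. With 540 women and f from 20% to 90%, power for R = 2.0 is still at least 99.6%.

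**Step 2: the relative risk that does have 80% power at 60% initiation.**

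| Split (high:low uptake) | N = 1200 |
|---|---|
| 10:90 | 1.22 |
| 25:75 | 1.16 |
| 50:50 | 1.14 |
| 75:25 | 1.17 |
| 90:10 | 1.28 |

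Check at 50:50, R = 1.141: p0 = 0.60/1.0705 = 0.5605, p1 = 0.6395. z = (0.0790 − 0.0554)/0.0282 = 0.84, which is power 0.80.

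Over the same splits the range is 1.16 to 1.33 at N = 900 and 1.22 to 1.47 at N = 540. A log-relative-risk Wald test at N = 1200 gives 1.14 to 1.33.

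**Step 3: the persistence sentence.** The plan's chain is 1200 × 0.60 = 720, × 0.75 = 540, × 0.70 = 378. So 378 is the numerator (women expected to be adherent), not the number whose adherence is compared. At a 70% rate, R = 2.0 needs p1 = 1.4/(1 + f), which exceeds 1 when f is below 40%. Among 540 women, 80% power corresponds to a relative risk of about 1.17 (50:50) to 1.36 (90:10). Using 378 as the number compared does not rescue the claim: power for R = 2.0 is then still above 99% for f from 40% to 90%.

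**The case against.** Read as a floor, the sentence can be defended. It speaks of 2.0 or greater, and power is indeed at least 80% wherever 2.0 is attainable and neither group is tiny. A reader might infer that the printed figure cannot be true at all; that goes too far, since a lower-uptake group of about 20 women would give 80%. Such a group is not plausible for an age or relationship split, so the pairing still does not describe what 1200 women deliver.

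The detectable values also depend on splits that the documents do not give. That stands. A rarer covariate moves them: with 95% of women in the higher-uptake group, the figure at N = 1200 is 1.43.

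The calculation is unadjusted, while SAP section 1 plans multivariable probit models with covariates chosen from causal diagrams. That also stands: adjusted analyses will have somewhat larger minimum detectable relative risks. Pregnant against postpartum status does not fit a cohort split either, because every woman is pregnant at enrolment and the status changes within each woman.

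For persistence, the 70% is assumed for adherence during at-risk periods among retained women, whereas the primary objective analysis covers all who initiated. The 1.17–1.36 range is therefore conditional on borrowing that rate.

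Finally, a reader might infer that the plan declares associations below 2.0 out of reach, or that null results will be judged against 2.0. No section says either. SAP 2.4 (Interpretation) still holds template prompts, SAP 2.2(5) compares head-counts only, and the primary Aim 1 analysis is descriptive.

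**Conclusion.** The point holds for initiation as an internal inconsistency. At the plan's own 60%, 1200 women have more than 99% power for a relative risk of 2.0 at any realistic split where 2.0 is possible, and 2.0 is impossible when the higher-uptake group is under 20%. The relative risk matching 80% power is about 1.14 to 1.28, given splits of 10:90 to 90:10, all 1200 women analysed and no adjustment. It stays well below 2.0 at the smaller assumed analysis sets. These figures apply to fixed between-woman covariates such as age and relationship status.

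The persistence sentence needs correcting for its denominator as well as its effect size.

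This should not be read as a finding that the study is underpowered. The error runs the other way, and no primary descriptive result depends on it.

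**What to change.** In protocol section 6 and SAP section 1:

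- **Initiation.** Replace the 2.0 sentence with the minimum detectable relative risk at 80% power and two-sided 0.05. State the 60% initiation rate, the assumed covariate split and the number actually analysed, which under the plan's own rule is the completers. The figures for 1200, 900 and 540 above can serve as a range until the completion rate is known.
- **Limits.** Say that the figures are unadjusted, so adjusted models will detect only somewhat larger relative risks. Say that they cover age and relationship status but not pregnant against postpartum status.
- **Persistence.** Present 378 as the expected number adherent, name the number compared, and restate the detectable relative risk. With 540 women and an assumed 70% rate it is about 1.17 (50:50) to 1.36 (90:10).
- **SAP 2.2(5).** Reword so that 1200, 720, 540 and 378 are expected counts, not sizes needed for 80% power.

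The cost is rewording two paragraphs and one list item. Enrolment, data collection and models stay as they are.
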